7.12 Blinding and unblinding

Given the nature of the intervention, it is not possible to blind participants or local research teams to treatment allocation. Self-reported outcomes will avoid observer bias. The lead statistician will be blinded to treatment allocation and the trial statistician, who is performing the analysis, will be unblinded to treatment allocation. Members of the TMG not involved in participant randomisation, intervention delivery, or performing disaggregated analyses will also be blinded to allocation.

7.13 Participant Payments

All participants will be offered a £20 voucher as a gesture of gratitude for completion of both Baseline and Day 5 Questionnaires. This will be offered to the participant upon completion of Day 5 questionnaires. The study centre will supply the vouchers in physical or digital format, to the site teams to disseminate to eligible participants.

We will also provide participating sites with trial branded pens. These will be given to participants who are allocated to the intervention, as an aid to completion of their adherence diary.

7.14 Change in participation status

Participants will remain in the trial unless they (or their Personal Consultee/PLR) choose to stop their participation, or they are unable to continue for a clinical reason. In the event that a clinician feels it is unsafe for a participant to continue in the study, agreement should first be sought from the PI. Any changes to a participant's continuation in the study should be recorded on the appropriate study document (e.g. Change of Permissions/Withdrawal Form). Trial specific guidance will be provided to participating sites on recording and reporting procedures.

The trial will retain any research data collected up to the point of stopping participation (or death) for analysis purposes. Furthermore, as advised in the trial participant information materials, the trial team will continue to collect relevant data about the patient's health from their electronic medical records unless they explicitly request otherwise.

It is of paramount importance to note that participants who do not wish to follow their randomised allocation , or where clinicians do not wish to adhere to the randomised allocation, should not stop their participation in the trial and they should continue to be followed up as per Protocol. Adherence to treatment allocation will be recorded and monitored via study data collection forms.

7.15 Communication with participants

An optional consent statement will be included to offer participants the opportunity to receive a summary of the trial results upon its completion. Updates on trial progress will be posted regularly on the study website, and all participants will be provided with the necessary access details to view this information.

8 SAFETY RECORDING AND REPORTING

8.1 Definitions

Adverse Event

An adverse event (AE) is any untoward or undesirable medical occurrence in a subject receiving treatment according to the protocol. This includes occurrences which are not necessarily caused by or related to administration of the research procedures.

Adverse Reaction

An adverse reaction (AR) is any undesirable experience that has happened to a subject that is suspected to be caused by the intervention.

Serious Adverse Event

A serious adverse event (SAE) is any adverse event which:

- results in death,
- is / was life threatening*,
- requires hospitalisation or prolongs an ongoing hospitalisation**,
- results in persistent or significant disability or incapacity,
- consists of a congenital anomaly or birth defect,

Other important medical events that may jeopardise the subject and may require medical or surgical intervention to prevent one of the outcomes listed above should also be classed as an SAE.

* "Life-threatening" in the definition of "serious" refers to an event in which the participant was at risk of death at the time of the event; it does not refer to an event which hypothetically might have caused death if it were more severe.

** "Hospitalisation" is defined as an unplanned overnight stay. Note, however, that the patient must be formally admitted – waiting in outpatients or an Emergency Department would not count as hospitalisation (even though this can sometimes be overnight). Planned hospital stays would not be counted as SAEs, nor would time in hospital for "social reasons" (e.g. respite care, the fact that there is no-one at home to care for the patient). Also, if patients had a day-case operation, this would not qualify as hospitalisation. However, if a planned operation was brought forward because of worsening symptoms, this would be considered as an SAE. Hospitalisations for the purpose of the intervention are an exception to SAE reporting unless complications occur.

Suspected Serious Adverse Reaction

A suspected serious adverse reaction (SSAR) is any serious adverse event that is suspected to be related to the intervention.

Suspected Unexpected Serious Adverse Reaction

A suspected unexpected serious adverse reaction (SUSAR) is serious adverse event that is not consistent with the defined anticipated or expected events (below) and is assessed as being possibly, probably or definitely related to the intervention.

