8.4 Reporting overview

Adverse event (AE)	Non-serious adverse events do not need to be recorded or reported unless they are considered to be possibly, probably, or definitely related to the use of the intervention. If a non-serious AE is considered to be possibly, probably, or definitely related to the intervention the AR should be recorded in the CRF and in the participant's clinical notes.
Adverse reaction (AR)	
Serious adverse event (SAE)	Record in safety reporting CRF and participant's clinical notes. Record assessment of causality, severity and seriousness. Report to trial team within 24h of becoming aware (who will report on to Sponsor within 24h).
Suspected unexpected serious adverse reaction (SUSAR)	Record in safety reporting CRF and participant's clinical notes. Record assessment of causality, severity and seriousness Report to trial team within 24h of becoming aware (who will report on to Sponsor within 24h). CI will report to REC within 15 days of becoming aware of the event.

All safety information, including information relating to safety events that are not subject to expedited reporting but are captured as trial endpoints, will be closely monitored by the DMSC throughout the trial. The DMSC will be provided with a report at least annually (unless specified by the DMSC).

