8.5 Anticipated events

Anticipated events are defined as safety events that are anticipated for this patient population. Although the investigational device poses minimal risk, adverse events are anticipated in this older, frailer population. The PI at each participating site (or appropriately delegated member of local site staff) is responsible for assessing all AEs and categorising whether they are serious, expected, and/or related.

The following events can be expected within trial participants:

- Pain
- Pulmonary complications
- Surgical emphysema
- Pneumothorax
- Delayed haemothorax
- Surgery for injuries present at enrolment
- Hospital admission complications, assessed by local PI as associated with frailty
- Prolonged hospitalisation due to social care needs

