8.6 Expectedness of events

Expected events are clinical outcomes that routinely occur when delivering the intervention.

The following events can be expected for patients treated with incentive spirometry:

- Dizziness or light-headedness
- Temporary increase in shortness of breath
- Altered breathing pattern

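### The SUSAR definition tests expectedness against the patient-population list as well as the device list, so a spirometer-related serious event in a section 8.5 category gets no expedited individual report to the REC

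*Protocol*

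**What the plan says.** Protocol section 8.1 sets two conditions for a SUSAR beyond seriousness. On expectedness, it "is serious adverse event that is not consistent with the defined anticipated or expected events (below". On causality, it "is assessed as being possibly, probably or definitely related to the intervention".

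The two lists that the definition points to have different bases. Section 8.5 concerns the patients: "Anticipated events are defined as safety events that are anticipated for this patient population". Its stated reason is that, although the device carries little risk, "adverse events are anticipated in this older, frailer population". It has eight entries, among them pulmonary complications, pneumothorax, surgical emphysema, delayed haemothorax and "Hospital admission complications, assessed by local PI as associated with frailty". No entry carries a limit on severity or on cause.

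Section 8.6 concerns the device: "Expected events are clinical outcomes that routinely occur when delivering the intervention". It has three entries: dizziness or light-headedness, a temporary increase in breathlessness, and altered breathing pattern.

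The reporting table in section 8.4 sends every SAE to the trial team within 24 hours of awareness, and the trial team passes it to the Sponsor within 24 hours. Only the SUSAR row adds a step to the ethics committee: "CI will report to REC within 15 days of becoming aware of the event".

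**The concern.** Whether an event is common after rib fracture in frail older people, and whether it is a known effect of the spirometer, are separate questions. The Protocol keeps them apart under two headings and then merges them in the SUSAR definition. Once an event has been judged related to the device, the relevant question is whether the device is known to cause it. A high background rate from the injury does not answer that.

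At stake is the one report that would put an individual suspected device harm before the REC promptly. The categories affected are not peripheral. Pneumothorax and the other pulmonary complications are components of the primary outcome (Table 2, section 6.7.1), so an adverse effect of the device on them would be the reverse of the benefit the trial is testing for. Section 11.3 plans no formal interim efficacy or futility analysis, which gives event-level safety reporting somewhat more weight.

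**Working it through.** No arithmetic applies. The check is to run the definition on cases.

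**Inputs.** The seriousness, causality and expectedness tests from section 8.1; the population list from 8.5; the device list from 8.6; the reporting routes from 8.4.

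**Step 1: the rule as written.** SUSAR = serious AND related AND NOT (on the 8.5 list OR on the 8.6 list).

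**Step 2: the rule with the population list removed.** SUSAR = serious AND related AND NOT (on the 8.6 list).

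**Step 3: apply both.** Every case below is taken as serious and judged related to the spirometer.

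| Serious, related event | In 8.5? | In 8.6? | SUSAR as written? | SUSAR on 8.6 alone? |
|---|---|---|---|---|
| Pneumothorax | Yes | No | No | Yes |
| Pulmonary complication | Yes | No | No | Yes |
| Delayed haemothorax | Yes | No | No | Yes |
| Admission complication attributed to frailty by the local Principal Investigator (PI) | Yes | No | No | Yes |
| Dizziness | No | Yes | No | No |
| Event on neither list | No | No | Yes | Yes |

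The two rules differ only in the first four rows. There the whole difference comes from the 8.5 limb of the definition. None of the eight entries in 8.5 appears by name in 8.6.

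**Step 4: follow the reporting route.** The first four cases are not SUSARs, so they fall in the SAE row of the 8.4 table: trial team, then Sponsor, with no REC step. Section 8.1 also defines a suspected serious adverse reaction, a class that would fit these events, but the 8.4 table has no row for it. No other event-level route to the REC is given.

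**Step 5: look for a rescue in the wording.** An assessor might call an unusually severe case inconsistent with the list. Section 8.5 sets no severity limit that would support this. It also introduces its own list as events that can be expected, which pulls the two ideas closer together.

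**The case against.** The strongest reply is that oversight of these events is largely intact, and most of that reply stands. Every SAE, related or not, goes to the trial team and on to the Sponsor in the two 24-hour steps, with causality recorded. The monitoring committee follows all safety information, receives a report at least annually (section 8.4) and meets about every six months (section 12.3). Section 13 allows the trial to be stopped on new safety information. The Protocol also takes a risk-adaptive approach (section 8.2) because it regards the device as safe and already in use. That approach can justify light recording of non-serious or unrelated events. It does not explain why a related serious event should count as expected because of the underlying injury.

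A reader might infer several stronger points that the documents do not support:

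- **That such an event can never reach the REC.** It can do so indirectly: by notification of an urgent safety measure within three days (section 8.7), or in the final report within one year of the end of the trial (section 15.3). Only the expedited individual report is lost.
- **That section 8.4 contradicts itself.** The sentence under the table mentions "safety events that are not subject to expedited reporting but are captured as trial endpoints". Non-serious pulmonary complications fit that description: they count towards the primary outcome, and if unrelated to the device they need no safety report. Read so, table and sentence agree, and no exemption for SAEs is implied.
- **That the frailty entry lets an unblinded PI remove almost any event.** It covers only hospital admission complications attributed to frailty, and it affects SUSAR status, not SAE reporting. What stands is that it rests on a local judgement and, as written, defeats SUSAR status even for an event judged definitely related.
- **That the device is mechanically likely to cause these harms.** The documents give no support for this. They describe sustained deep breaths and minimal risk.

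**Conclusion.** The concern holds in a limited form. As written, the definition classes a whole set of related serious events as not unexpected because they are common in the population, and so withholds the 15-day REC report from them. Sponsor and committee oversight is unaffected, as are the primary outcome definition, estimand, sample size and analysis.

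The size cannot be given as a count. It is tempting to take the planned complication rates (50% control, 30% intervention) as a measure of exposure. Those rates cover all severities and both arms, and control participants should not be issued a spirometer. The documents give no rate for events that are both serious and device-related. The number may well be small; the point is how such an event would be handled if it occurred.

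The conclusion assumes that the definition is applied literally, that the word pointing to the text below it refers to both 8.5 and 8.6, and that no separate safety document overrides section 8. It is a correction of wording with a patient-safety purpose and is worth making.

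**What to change.** 1. In section 8.1, delete the words 'anticipated or' from the SUSAR definition and point it to section 8.6, so that expectedness of a related SAE is judged against the intervention list only.
2. In section 8.5, add a sentence saying that the list describes background events in this population and does not make a serious event expected once it has been judged related to the intervention.
3. Carry the same wording into the safety reporting form and site training where they repeat the definition.

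Leave the 24-hour reporting of all SAEs unchanged. In particular, section 8.5 should not become a list of SAEs exempt from it: the Protocol has no such exemption, and adding one would weaken present reporting.

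The cost is two sentences in section 8 and matching edits to the form and training material, through the amendment route in section 15.4. Extra reporting arises only when a serious event is judged related and is not on the 8.6 list.

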8.2 Approach – risk adaptive of following GCP

This study is following a risk-adaptive approach to safety reporting because the intervention being studied has already been proven to be safe and is already in use in standard medical care.

8.3 Reporting period

Local research teams are responsible for assessing all AEs that they become aware of for their participants from the time of enrolment until the 30 day follow-up.

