6.6.5 Adherence

A paper diary will be provided to participants in the intervention arm to record adherence to intervention use during their inpatient admission. These will be collected by local site staff on or after day 5 post randomisation, or on discharge, whichever is sooner, and data entered to the study database.

A CRF will also be provided to record any observed adherence, where feasible, in recognition of variable participant adherence to diaries in previous clinical trials (22). This includes any use of a spirometer in the participants randomised to the control arm (usual care). In cases where both participant diaries and staff-collected adherence data are available, participant entries will take precedence in the event of discrepancies; however, if only staff-collected data are complete, those will be used.

Participants in the intervention arm will be classed as adherent if they undertake a minimum of two incentive spirometer sessions a day, for a minimum of three days, in the five days post randomisation.

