6.7 Outcomes

6.7.1 Primary outcome

The primary outcome is a binary measure of the onset of one or more new pulmonary complications within five days of randomisation. This will be adapted from the outcome proposed by the European Society of Anaesthesiology and Intensive Care Medicine as a consensus definition (Table 2) (23). Patients with evidence of pulmonary complications prior to randomisation will not meet the primary outcome. Any deaths occurring within the first 5 days following randomisation will meet the criteria for the primary outcome.

Table 2: Pulmonary Complications

Complication	Definition
Respiratory Infection	Patient has received antibiotics for a suspected respiratory infection and met one or more of the following criteria: new or changed sputum, new or changed lung opacities, fever, white blood cell count $>12 \times 10^9 \text{ l}^{-1}$

Respiratory failure	PaO ₂ <8kPa (60mmHg) on room air, a PaO ₂ :FiO ₂ ratio <40kPa (300mmHg) or arterial oxyhaemoglobin saturation measured with pulse oximetry <90% (or <88% for patients with known chronic respiratory disease) and requiring oxygen therapy
Pleural effusion	Chest radiograph demonstrating blunting of the costophrenic angle, loss of sharp silhouette of the ipsilateral hemidiaphragm in upright position, evidence of displacement of adjacent anatomical structures or (in supine position) a hazy opacity in one hemithorax with preserved vascular shadows
Atelectasis	Lung opacification with a shift of the mediastinum, hilum or hemidiaphragm toward the affected area, and compensatory over-inflation in the adjacent non-atelectatic lung
Pneumothorax	Air in the pleural space with no vascular bed surrounding the visceral pleura
Bronchospasm	Newly detected expiratory wheezing treated with bronchodilators
Aspiration pneumonitis	Acute lung injury after the inhalation of regurgitated gastric contents

Primary outcome data will be collected by research practitioners from inpatient hospital records at five days and reviewed/confirmed by the local Principal Investigator. For the small number of patients discharged in the interim, online GP records (routinely available at recruiting sites) will be checked for evidence of pulmonary related events (e.g., pneumonia).

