6.7.2 Secondary outcomes

- Patient reported breathlessness at baseline and 5 (+2*) days (The Dyspnea-12 Questionnaire)
- Patient reported pain at baseline and 5 (+2*) days (Numeric Pain Rating Scale)
- Length of initial stay up to 30 days post randomisation
- Admission to Critical Care up to 30 days post randomisation
- Mortality up to 30 days post randomisation
- Hospital readmission within 30 days of randomisation

*Pain and breathlessness scores will be collected on day 5 where possible but a +2-day window will be accepted to accommodate lack of weekend staffing.

It is anticipated that the majority of patients will remain inpatients on day 5 and patient reported outcome measures can be collected in person by local site staff. For any patients discharged prior to day 5, follow-up can be completed remotely by telephone. The Dyspnea-12 questionnaire and Numeric Pain Rating Scale are both possible to complete by telephone. The researcher will make (up to) three contact attempts. If no response is received, the questionnaires will be marked as missing.

As the Dyspnea-12 Questionnaire includes a question pertaining to depressive symptoms, any participant identified as indicating severe levels of depression will be encouraged by local site staff to seek further evaluation or support from their treating clinician or General Practitioner.

The NPRS has been reported suitable to use with people with mild to moderate cognitive impairment (²⁴). We are unable to find a breathlessness patient reported outcome, suitable for trauma, that has been validated for cognitive impairment in this population. It is recognised that some data for this secondary outcome may be missing for those with mild to moderate cognitive impairment. However, “here and now” symptom self-reporting tools have been shown to be valid and reliable in persons with mild cognitive impairment in previous literature (²⁵) and use of the dyspnea-12 questionnaire in this

trial is supported by our patient and public involvement representatives. Secondary outcomes measured up to 30 days post randomisation will be collected by research staff from their hospital's electronic patient record.

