7.8 Schedule of assessments and data collection

Activity/ Assessment	Enrolment	Randomisation/ Baseline	Initial teaching session †	Additional teaching†*	Follow-up			As required
Time point	Day 0 (-1)	Day 0	Day 0 (+2)	Day 0 (+≤5)	Day 5	Day 5(+2)	Day 30	Up to Day 30
Screening	X							
Consent	X							
Sociodemographic Details		X						
Injury Details		X						
Co-morbidities		X						
Clinical Frailty Scale (Rockwood)		X						
Initial incentive Spirometry Teaching Session †			X					
Up to 2 additional incentive spirometry teaching sessions†				X*				
Adherence					X			
Primary outcome					X			
Secondary outcomes (PROMS)		X				X		
Length of stay (hospital and critical care/ HDU admission)							X	
Details of re-attendances to A&E or unplanned re-admissions							X	
Mortality						X	X	

Safety Reporting CRF								X
Change of Status CRF								X

t Intervention arm only

**only if required*

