For patients who have mild/moderate cognitive impairment (e.g. due to Alzheimer's disease), the PROMs may be completed with the assistance of a researcher/member of the clinical team (or person with caring responsibility if/where feasible); if in such participants it becomes unfeasible to complete the PROMS (or elements of it), site staff should record this in the 5-day CRF.

Participants who have transferred to a different hospital or who have been discharged from hospital at 5-days post-randomisation (+2 days):

Follow up will be completed remotely using a range of available methods to suit the participant's preferences and location (e.g. via telephone or site staff at receiving hospital if transferred to another trial site). If the participant does not have capacity, where possible, then a consultee (and/or person with caring responsibility) will be asked to assist the participant to complete the PROMS. If it is not feasible for the participant to complete (part of) the PROMs, site staff should record this in the 5-day CRF.

7.11 Follow up Data Collection at Day 30

CRF (site staff): A delegated site staff member will complete the 30-day CRF. Data capture on this CRF will include (but is not limited to):

- Hospital admission details, including discharge status and date (where applicable)
- Mortality data
- Resource use e.g. admission to critical care (including HDU) during index admission; any unplanned readmissions within 30 days

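### Serious adverse events that are not trial endpoints have no scheduled check in either arm, and the spirometer arm's extra early contacts could make their detection modestly uneven

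*Protocol*

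**What the plan says.** Safety capture is driven by awareness. Section 8.3 asks sites to take responsibility for "assessing all AEs that they become aware of for their participants from the time of enrolment until the 30 day follow-up". In 8.4 the clock for a serious event also starts at awareness: "Report to trial team within 24h of becoming aware". In the schedule of assessments (7.8) the row "Safety Reporting CRF" is marked only in the as-required column that runs up to Day 30, with no mark at Day 5 or Day 30.

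Several classes of serious event are nevertheless collected on schedule in both arms:

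- Day 5 (6.7.1): "Primary outcome data will be collected by research practitioners from inpatient hospital records at five days". This covers the complications in Table 2 and any death in the first five days, and the local Principal Investigator confirms it.
- Day 30 (7.8): "Details of re-attendances to A&E or unplanned re-admissions", together with mortality and length of stay.
- Day 30 CRF (7.11): "Resource use e.g. admission to critical care (including HDU) during index admission; any unplanned readmissions within 30 days".
- Source (6.7.2): "Secondary outcomes measured up to 30 days post randomisation will be collected by research staff", using the hospital's electronic record.

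The contacts that belong to the intervention arm alone are one initial teaching session (Day 0, up to two days later), up to two more by Day 5 if required (6.6.3, 7.8), and collection of the adherence diary at Day 5 or later, or at discharge if that comes sooner (6.6.5). Local research teams are not blinded (7.12), and site staff also judge seriousness and relatedness (8.5).

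**The concern.** Some serious events fall outside the scheduled collection. Examples are a non-pulmonary complication that prolongs the stay, a life-threatening episode managed without critical-care admission, and a delayed haemothorax (listed in 8.5 as anticipated but not named in Table 2). For these, the protocol fixes no moment at which anyone must ask whether an event occurred. An absent Safety Reporting CRF can mean either that there was no event or that nobody looked.

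If detection depends on awareness, it depends on contact, and before about Day 5 trial contact is heavier in the spirometer arm. Any resulting imbalance would appear as an excess of serious events with the spirometer.

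Under 8.4, non-serious events are recorded only when judged related to the intervention. Serious events are therefore the only adverse-event class recorded in both arms whatever the cause, and so the only one that allows a comparison between arms. These counts go to the combined monitoring and steering committee, and section 13 allows the trial to stop early on new safety information.

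**Working it through.** **The plan's own figure.** The only design calculation is the sample size (6.7.4): 50% against 30%, 90% power, 5% alpha (two-sided assumed).

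- Per arm: n = [1.960 × √(2 × 0.40 × 0.60) + 1.282 × √(0.50 × 0.50 + 0.30 × 0.70)]² / 0.20² = 124, so 248 in total.
- With 10% attrition: 248 / 0.90 = 275.6, so 276.

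Both stated figures reproduce. The point does not depend on them, except that 276 / 2 = 138 per arm is used below.

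**Which serious events have a scheduled look that is the same in both arms?**

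| Type of event | Scheduled look | Depends on awareness? |
|---|---|---|
| Death | Day 5 and Day 30 | No |
| Table 2 pulmonary complication by Day 5 | Day 5 record review | No |
| Critical-care/HDU admission | Day 30 | No |
| Unplanned readmission, A&E re-attendance | Day 30 | No |
| Non-pulmonary complication prolonging the stay | Duration of stay only, not its cause | Yes |
| Life-threatening episode without critical-care admission | None | Yes |
| Delayed haemothorax without critical care, readmission or death | None by name | Yes |
| Other important medical events (8.1) | None | Yes |

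**Which contacts differ by arm?**

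- Initial teaching: intervention arm only, certain.
- Additional teaching: intervention arm only, zero to two sessions.
- Diary collection: intervention arm only, at about Day 5 or at discharge.
- Day 5 (+2) questionnaires: both arms.
- Observed-adherence form (6.6.5): "A CRF will also be provided to record any observed adherence, where feasible". The same section says it also records spirometer use by control participants, so it covers both arms.
- After about Day 5: no scheduled contact differs by arm.

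The uneven window therefore runs from randomisation to about Day 5. The lack of a fixed look at the residual class runs to Day 30, but equally in both arms after that window.

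**Illustration of size.** The protocol gives neither a serious-event rate nor a detection rate, so every input here except 138 is an assumption. Let p be the true risk of an awareness-dependent serious event, equal in both arms. Let d_S and d_C be the detection probabilities in the spirometer and control arms.

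- Expected counts: 138 × p × d_S and 138 × p × d_C.
- Observed ratio under no true difference: d_S / d_C.

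With d_S = 0.95, the table gives spirometer against control counts, with the excess in brackets:

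| p | d_C = 0.90 (ratio 1.06) | d_C = 0.80 (ratio 1.19) | d_C = 0.70 (ratio 1.36) |
|---|---|---|---|
| 5% | 6.6 v 6.2 (0.3) | 6.6 v 5.5 (1.0) | 6.6 v 4.8 (1.7) |
| 10% | 13.1 v 12.4 (0.7) | 13.1 v 11.0 (2.1) | 13.1 v 9.7 (3.4) |
| 20% | 26.2 v 24.8 (1.4) | 26.2 v 22.1 (4.1) | 26.2 v 19.3 (6.9) |

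With equal detection the excess is zero.

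**Dilution across all serious events.** If a share s of serious events is captured on schedule in both arms, the overall ratio is [s + (1 − s) × d_S] / [s + (1 − s) × d_C]. With s = 0.5 (assumed), d_S = 0.95 and d_C = 0.80, this is 0.975 / 0.900 = 1.08, against 1.19 for the residual class alone.

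**Against chance.** Take 26.2 v 22.1 of 138, that is 19% v 16%. The difference is 3 points, with standard error √[(0.19 × 0.81 + 0.16 × 0.84) / 138] = 4.6 points. A bias of this size would be hidden within sampling variation.

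**The case against.** The strongest reply has four parts.

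- **Awareness is built in for the main classes.** Two record reviews, the same in both arms, cover deaths, early pulmonary complications, critical care and readmission. This stands. A reader might infer from 8.3 alone that all serious events are left to chance and that nothing is checked on schedule, but 6.7.1, 7.8 and 7.11 contradict that.
- **The contact imbalance is small.** Only one extra teaching session is certain, diary collection falls close to the Day 5 questionnaire contact that both arms have, and most participants are expected to be inpatients at five days, so clinical staff should document serious events in either arm. This also stands and limits the likely effect. It does not remove the gap, because an event in the clinical notes enters the trial data only if someone in the research team meets it.
- **The approach is deliberate and monitored.** Section 8.2 declares risk-adaptive reporting for a device already in use, no between-arm test of serious events is planned, and 10.4 names adverse-event reporting among the typical monitoring checks. But a reduced recording burden is no reason for uneven recording. Section 10.4 also says the trials centre will not compare source data with the database unless there is good reason, so an event never entered would be hard to flag.
- **The CRFs are not shown.** The Day 30 list in 7.11 is expressly not exhaustive, so a prompt may already exist. That is possible. The protocol's own schedule would still need to show it.

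**Conclusion.** The point holds for one class only: serious events that are not already trial endpoints. For these, capture rests on the awareness of unblinded staff, no fixed time point exists, and early contact is somewhat heavier in the spirometer arm. A modest detection difference is possible, but its direction and size cannot be established from the protocol. The illustrative excess of 0.3 to 6.9 participants rests on assumed risks of 5% to 20% and assumed detection of 95% against 90% to 70%.

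Three stronger readings are not supported:

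- The ratios of 1.06 to 1.36 do not describe serious events overall, because deaths, early pulmonary complications, critical-care admissions and readmissions are collected equally in both arms.
- The observed-adherence form is not a contact unique to the spirometer arm.
- Missed control-arm events are not necessarily lost. Record-based collection continues after participation stops unless refused (7.14), and source data are kept for at least five years (9.6), so a later record review remains possible.

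The primary analysis and the sample size are untouched. This is a low-severity improvement, worth making because it is cheap.

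**What to change.** - **Section 7.8:** mark a safety check at Day 5 and at Day 30 for both arms, as a mandatory yes/no item on the existing CRFs asking whether any SAE has occurred since randomisation (Day 5) or since the last check (Day 30). Complete it from the hospital record already being reviewed for the primary and 30-day outcomes, and reconcile each answer with the Safety Reporting CRF.
- **Section 8.3:** state that SAEs are actively sought at these two checks in both arms.
- **Section 8.4:** keep the 24-hour report on awareness unchanged, alongside the two checks.

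If the CRFs already carry such an item, only 7.8 and 8.3 need aligning with them.

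Cost: one item on each of two existing forms, a few minutes per participant, and some additional SAE reports. It needs no new visit or staff and no change to the sample size, and it is compatible with the risk-adaptive approach in 8.2.
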